13.2.7 Clinical Laboratory Tests

All tests listed below will be performed as outlined in the Study Events Flow Chart (Section 6). In addition, laboratory safety tests may be performed at various unscheduled time points, if deemed necessary by the PI or designee.

Hematology

- Hemoglobin
- Hematocrit
- Total and differential leukocyte count
- Red blood cell count
- Platelet count

Coagulation

- PT/INR
- aPTT

Urinalysis⁺

- pH
- Specific gravity
- Protein***
- Glucose
- Ketones
- Bilirubin
- Blood***
- Nitrite***
- Urobilinogen
- Leukocyte esterase***

Serum Chemistry*

- BUN
- Bilirubin (total and direct)
- ALP
- AST
- ALT
- LDH
- Albumin
- Sodium
- Potassium
- Chloride
- Glucose (fasting)
- Creatinine**

Additional Tests

- HIV test
- HBsAg
- HCV
- Urine or saliva drug screen
 - Opiates
 - Amphetamines
 - Cocaine
 - Cannabinoids
- Urine, breathalyzer, or saliva alcohol screen
- Serum pregnancy test (for females only)
- FSH (for postmenopausal females only)

* Serum chemistry tests will be performed after at least a 4-hour fast; however, in case of dropouts or rechecks, patients may not have fasted for 4 hours prior to the serum chemistry sample is taken.

** At screening, creatinine clearance will be calculated using the Cockcroft-Gault formula.

*** If urinalysis is positive for protein, blood, nitrite and/or leukocyte esterase, a microscopic examination (for red blood cells, white blood cells, bacteria, casts, and epithelial cells) will be performed.

⁺ For anuric patients, urinalysis may not be performed.

13.2.8 Adverse Events

13.2.8.1 Adverse Event Definition

AE will be defined as any untoward medical occurrence during the study, associated or not with the use of xisomab 3G3 in the study patients, whether or not considered drug related. TEAE is an AE that occurs after administration of the study drug or placebo.

A suspected adverse reaction means any AE for which there is a reasonable possibility that the drug caused the AE. Reasonable possibility means there is evidence to suggest a causal relationship between the drug and the AE.

An AE can therefore be any unfavorable and unintended sign (including an abnormal laboratory finding), symptom, or disease temporally associated with the use of a medicinal (investigational) product, whether or not related to the study drug. ([FDA Guidance, 2012](#))

Prolonged aPTT is an expected pharmacodynamic effect of xisomab 3G3 and will, therefore, not be considered an AE.

13.2.8.2 Monitoring

Patients will be monitored for AEs from check-in through completion of the study. Patients will be asked how they are feeling once per day during confinement and at each return/follow-up visit.

AEs (whether serious or non-serious) and clinically significant abnormal laboratory test value(s) will be evaluated by the PI or designee and treated and/or followed up until the symptoms or value(s) return to normal, or acceptable levels, as judged by the PI or designee.

Treatment of serious adverse events (SAEs) will be performed by a licensed medical provider, either at the CRU or at a nearby hospital emergency room. Where appropriate, medical test(s) and/or examination(s) will be performed to document resolution of event(s). Outcome may be classified as resolved, improved, unchanged, worse, fatal, or unknown (lost to follow-up).

13.2.8.3 Reporting

All AEs that occurred during this clinical study (i.e., before, during, and after exposure of ESRD patients to xisomab 3G3) will be recorded. This design is to improve Sponsor ability to obtain reliable initial information about drug safety yet reducing the number of study patients needed to generate useful data.

Adverse events and SAEs that are related to study participation (e.g., protocol-mandated intervention) will be recorded from the time the patient check-in until study completion. All other AEs and SAEs will be recorded from Day -8 until exit from the study.

AEs will be coded using the most current MedDRA® available at Celerion.

The PI or designee will review each event and assess its relationship to study drug (likely, probably, possibly, unlikely, or unrelated) and severity. The date and time of onset, time relationship to drug dosing, duration, and outcome of each event will be noted.

Relationship of AE:

The relationship of each AE to the study drug will be assessed using the following definitions:

| | |
|-----------|--|
| Unrelated | 
 The adverse event must clearly be caused by the participants clinical state, or the study procedure/conditions Definitely not related to drug Temporal sequence of an adverse event onset relative to administration of drug not reasonable Another obvious cause of an adverse event |
| Unlikely | 
 Time sequence is unreasonable There is another more likely cause for an adverse event |
| Possibly | 
 Corresponds to what is known about the drug Time sequence is reasonable Could have been due to another equally, likely cause |
| Probably | 
 Is a known effect of the drug Time sequence from taking drug is reasonable Ceases on stopping the drug Cannot be reasonably explained by the known characteristics of the participants clinical state |
| Likely | 
 Is a known effect of the drug (e.g. listed in IB) Time sequence from taking drug is reasonable Event stops upon stopping drug, event returns upon restarting drug 
Note: Prolonged aPTT is an expected pharmacological effect of xisomab 3G3 and will, therefore, not be considered an AE.
 |

Severity of AE:

Severity rating used during the study will be based on the toxicity grading scale tables present in the FDA (Center for Biologics Evaluation and Research) toxicity grading scale for healthy volunteers 4-point severity scale (Grade 1, 2, 3 and 4). ([FDA Guidance 2007](#))

The following definitions for rating severity will be used for AEs not identified in the guidance:

| | |
|--|--|
| Mild (Grade 1) | The AE does not interfere with daily activity |
| Moderate (Grade 2) | The AE interferes with daily activity, but no medical intervention is required |
| Severe (Grade 3) | The AE prevents daily activity and requires medical intervention |
| Potentially Life-threatening (Grade 4) | Emergency room visit or hospitalization is required |

13.2.8.4 Serious Adverse Event

If any AEs are serious, as defined by the Food and Drug Administration (FDA) Code of Federal Regulations (CFR), Chapter 21, special procedures will be followed. All SAEs will be reported to the Sponsor via fax or e-mail within one working day of becoming aware of the event, whether or not the serious events are deemed drug-related. All serious event reporting will adhere to 21 CFR 312.32 for Investigational New Drugs (IND) and to the Guidance for Industry and Investigators: Safety Reporting Requirements for INDs and BA/BE, dated December 2012. The institutional review board (IRB) will be notified of the Alert Reports as per FDA regulations.

A SAE is any AE or suspected adverse reaction that in the view of either the PI (or designee) or Sponsor, results in any of the following outcomes: Death, a life-threatening adverse event, inpatient hospitalization or prolongation of existing hospitalization, a persistent or significant incapacity or substantial disruption of the ability to conduct normal life functions, or a congenital anomaly/birth defect. Important medical events that may not result in death, be life-threatening, or require hospitalization may be considered serious when, based upon appropriate medical judgment, they may jeopardize the patient or subject and may require medical or surgical intervention to prevent one of the outcomes listed in the above definition. Examples of such medical events include allergic bronchospasm requiring intensive treatment in an emergency room or at home, blood dyscrasias or convulsions that do not result in inpatient hospitalization, or the development of drug dependency or drug abuse.

Life-threatening is defined as an AE or suspected adverse reaction that in the view of the PI (or designee) or Sponsor, its occurrence places the patient or subject at immediate risk of death. It does not include an AE or suspected adverse reaction that, had it occurred in a more severe form, might have caused death.

Unexpected is defined as an AE or suspected adverse reaction that is not listed in the IB or is not listed at the specificity or severity that has been observed; or is not consistent with the risk information described in the general investigational plan or elsewhere in the current application, as amended.

If a SAE occurs to a patient on this study, contact the Sponsor personnel listed in [Section 3](#).

13.3 Hemodialysis Procedure and Blood Clots in the Dialyzer Cartridge

Patients will undergo hemodialysis 3 times a week as delineated in the Study Events Flow Chart ([Section 6](#)). For each patient, the hemodialysis will last at least 3 hours as per patient standard schedule which will be the same throughout the study.

Patients undergoing heparin-free hemodialysis may be at higher risk of developing clots within the hemodialysis circuit. In order to monitor clotting within the HD circuit, venous pressure will be continuously monitored. Should clotting within the dialyzer occur, site standard operating procedures will be followed to replace the clotted dialyzer and resume hemodialysis under the supervision of the PI, if appropriate. It is important to note that replacement of the dialyzer cartridge is a safe procedure for the patient. While studies

suggest that there is no risk of thromboembolic complications should this occur, clotting of the dialyzer circuit could result in up to ~228 mL of blood loss.

The hemoglobin levels will be followed more closely.

If the patient clots the hemodialyzer twice they may be discontinued from the study at the discretion of the PI. If the patient fully clots the hemodialyzer, the continuation of the patient in the study will be at the PIs discretion.

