| | Hours → | | start | end | start | end | start |
| Safety Evaluations | | | | | | | |
| Abbreviated Physical Examination ^{e:} | | | | | | | X ^{r:} |
| Weight | | X ^{f:} | X ^{g:} | X ^{f:} | X ^{g:} | X ^{f:} | X ^{g:} |
| 12-Lead Safety ECG | | | | | | | X ^{r:} |
| Vital Signs (HR, BP, RR, and T) | | X ^{f:} | | X ^{f:} | | X ^{f:} | X ^{r:} |
| Bleeding of Access Site | | | | | | | X ^{g:} |
| Hem, Serum Chem ^{h:} , and UA ^{i:} | | | | | | | X ^{r:} |
| Coagulation ^{j:} | | | | | | X ^{f:} | X ^{g:} |
| Platelet Count ^{s:} | | | | | | X ^{f:} | X ^{g:} |
| Serum Pregnancy Test (♀ only) | | | | | | | X ^{r:} |
| AE Monitoring | | | | X | | | X |
| ConMeds Monitoring | | | | X | | | |
| Study Drug Administration / PK/PD/Immunogenicity | | | | | | | |
| Blood for free xisomab 3G3 PK | | | | | | | X ^{r:} |
| Blood for free xisomab 3G3 PD (aPTT) ^{s:} | | X ^{o:} | | X ^{o:} | | | |
| Blood for Immunogenicity | | | | | | | X ^{r:} |
| Other Procedures | | | | | | | |
| Blood BUN and Potassium (for Kt/V and URR) | | | | | | X ^{f:} | X ^{g:} |
| Dialysate Analysis | | | | | | X ^{k:} | X ^{k:} |
| Visual Assessment and Processing of Dialyzer Membrane | | | | | | | X ^{l:} |
| Return Visits | | | X | | X | | X |

- a: For details on Procedures, refer to [Section 13](#)
- b: Within 28 days prior to Day -8.
- c: Patients will be admitted to the CRU on Day -8, at the time indicated by the CRU and will remain confined up to Day 6 or prior early termination.
- d: Patients will undergo hemodialysis 3 times a week, on Day -7, Day -5, Day -3, and Day 1, Day 3, Day 5, Day 8, Day 10, and Day 12. For each patient, the hemodialysis will last at least 3 hours as per patient standard schedule which will be the same throughout the study.
- e: Symptom-driven physical examination may be performed at other times, at the PI's or designee's discretion.
- f: To be performed ~ 1 hour prior to the start of hemodialysis.
- g: To be performed at the end of hemodialysis.
- h: Samples for serum chemistry will be obtained following a fast of at least 4 hours, however, in case of dropouts or rechecks, patients may not have fasted for 4 hours prior to the serum chemistry sample is taken.
- i: For anuric patients, urinalysis may not be performed.
- j: Coagulation parameters (activated partial thromboplastin time [aPTT], prothrombin time [PT], and international normalized ratio [INR]).

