8.4.2 Rationale for the Dose Selection

Doses of 0.25 mg/kg and 0.5 mg/kg were selected for this phase 2 study in order to provide adequate PD and PK characterization but still allowing a safety margin should the results differ in this population compared to healthy subjects. The 0.25 mg/kg xisomab 3G3 dose is 2.5-fold higher than the lowest dose in the FIH study. The 0.1 mg/kg dose in the FIH study had a short and modest, yet detectable PD effect (several seconds of temporal aPTT prolongation). The 0.25 mg/kg dose is expected to provide an initial plasma concentration that is within the range of average FXI concentration, the molecular target of xisomab 3G3, in human subjects, and may approach saturation in some individuals after full distribution. Therefore, it has the potential to exert brief pharmacological (anti-inflammatory, antithrombotic) activity, possibly lasting up to a day, until elimination of the antibody and hepatic FXI secretion that neutralizes the antibody.

The 0.5 mg/kg dose was safely administered in the FIH study and allowed adequate characterization of the PK profile in healthy adults. In addition, following a 0.5 mg/kg a prolongation of aPTT was seen, with highest values measured at 24 hours postdose and having a sustained effect for at least 72 hours postdose. The 0.5 mg/kg xisomab 3G3 dose is expected to provide, after complete distribution, a plasma concentration that is approximately twice the average human plasma concentration of the FXI antigen. Therefore, this dose is expected to be overcome by FXI generation later, and have pharmacological activity that lasts longer than the lower dose level.

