8.5 Risks and/or Benefits to Patients

ESRD patients are often ill, and are prone to a variety of adverse events on or off HD, ranging, for example, from infections to hypertension to bleeding to thromboembolism to acute ischemic cardiovascular emergencies, even if they are apparently stable on chronic HD. A temporal and modest increase in blood pressure was observed in one study subject in the FIH study after xisomab 3G3 administration, and the event was deemed potentially related to the study drug.

Xisomab 3G3 is a purified protein produced by recombinant DNA technology in a mammalian cell culture system, and these types of drugs can, occasionally and unpredictably evoke acute allergic reactions. Some ESRD patients develop chronic HD- and uremia-related moderate hemorrhagic diathesis or hemostasis impairment. Even though currently available data do not indicate a hemostatic function for the FXI/FXII interaction, there remains a theoretical possibility of contact activation-mediated enhancement of hemostasis. Thus, the hemostatic safety of xisomab 3G3 in the complex conditions of ESRD and chronic HD is not yet known. The safety monitoring practices employed by this protocol (i.e., 12-lead ECG, vital signs, blood pressure, clinical laboratory tests, AE questioning, vascular access site (AV fistula or AV graft) monitoring, and physical examination) are adequate to protect the patients' safety and should detect all expected and unexpected treatment-emergent AEs (TEAEs). In addition, the cohorts will be dosed in a sequential manner, starting with the lower dose level, Cohort 1.

Patients undergoing heparin-free HD may be at higher risk of developing clots within the hemodialyzer. Should this occur, site standard operating procedures will be followed to replace the clotted dialyzer and resume HD under the supervision of the PI. It is important to note that replacement of the dialyzer cartridge is a safe procedure for the patient. While studies suggest that there is no risk of thromboembolic complications should this occur, clotting of the dialyzer circuit could result in up to ~228 mL of blood loss.

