10.1.1 Confinement and Follow-Up

Patients will be housed on Day -8, at the time indicated by the CRU, until after completion of study procedures on Day 6 as indicated in the Study Events Flow Chart ([Section 6](#)). Patients will return to the CRU as per the Study Events Flow Chart ([Section 6](#)) for additional HD sessions and study procedures. At all times, a patient may be required to remain at the CRU for longer at the discretion of the Principal Investigator (PI) or designee.

All patients who received the study drug or placebo (including patients who terminate the study early) will undergo follow-up procedures at the CRU approximately 12 days after dosing.

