13 STUDY ASSESSMENTS AND PROCEDURES

The Study Events Flow Chart ([Section 6](#)) summarizes the clinical procedures to be performed at each visit. Individual clinical procedures are described in detail below. Additional evaluations/testing may be deemed necessary by the PI or designee and/or the Sponsor for reasons related to patient safety.

For this study, the primary assessment is the safety and tolerability. Safety will be determined by evaluating physical examinations, vital signs, ECGs, clinical laboratory parameters, including but not limited to, hematology, serum chemistry profile, coagulation, urinalysis, vascular access site reaction, and AEs as outlined in the Study Events Flow Chart ([Section 6](#)).

Any nonscheduled procedures required for urgent evaluation of safety concerns take precedence over all routine scheduled procedures.

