## **8.4 Clinical Laboratory Tests (Serum Chemistry, Hematology, Coagulation and Urinalysis)**

Safety serum chemistry, hematology and urinalysis tests are performed at Screening, Day -8 check-in, Day 1 predose, Day 6 and Day 12. For anuric patients, urinalysis may not be performed. Platelet count are collected at start and end of HD on Days -7, -5, -3, 1, 3, 5 and 12 and on Day 6. Platelet count are collected at start and end of HD on Days -7, -5, -3, 1, 3, 5 and 12 and Day 6. aPTT results are presented and discussed in the PD Section 7.2.

Out-of-range values and clinically significant results will be listed.

For all numeric laboratory values, descriptive statistics will be presented for each laboratory test by assessment time point and treatment. Change from baseline will be summarized in a similar manner. Baseline is defined as the result closest and prior to

dose which may include unscheduled results. This will typically be the result collected at predose on Day 1. Postdose unscheduled events or early termination results will not be included in summaries.

For each laboratory test, a shift table will be developed to compare the frequency of the results at baseline (above normal, normal, or below normal) with the respective postdose results.

Coagulation parameters and platelet count will be listed and presented together since they have the same timepoints. Urinalysis test results will be listed only.

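### No hemoglobin is scheduled for about 120 h after dosing, although pre-dialysis platelet samples already drawn on Days 3 and 5 could supply it cheaply

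*Protocol*

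**What the plan says.** SAP 8.4 sets the hematology schedule: "Safety serum chemistry, hematology and urinalysis tests are performed at Screening, Day -8 check-in, Day 1 predose, Day 6 and Day 12". The flow chart (Protocol 6) agrees for the period after dosing, with marks at Day 1 predose and at Day 6 discharge, then at Day 12. Platelets are sampled more often: "Platelet count are collected at start and end of HD on Days -7, -5, -3, 1, 3, 5 and 12 and on Day 6". For the pre-dialysis samples, flow chart footnote f gives the timing: "To be performed ~ 1 hour prior to the start of hemodialysis". Protocol 13.2.7 lists hemoglobin and platelet count in one hematology panel, and footnote s takes the platelet count from the hematology sample when both are due.

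Protocol 13.3 says that clotting of the circuit could cost up to about 228 mL of blood, and then: "The hemoglobin levels will be followed more closely". It gives no time point. Protocol 8.5 says that "the hemostatic safety of xisomab 3G3 in the complex conditions of ESRD and chronic HD is not yet known". On duration of action, Protocol 8.4.2 describes the 0.5 mg/kg dose in healthy subjects as "having a sustained effect for at least 72 hours postdose". For 0.25 mg/kg it expects activity for possibly up to a day.

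**The concern.** Hemoglobin is the direct measure of blood loss, whether from a clotted circuit or from bleeding that nobody sees. The plan leaves it unmeasured by schedule through the first five days after a first dose in this population, with dialysis run without heparin on three of those days. A clotted dialyzer is noticed and can prompt a test. Slow or hidden bleeding may not be, and a discretionary test needs a prompt. The samples that could close much of the gap are already being drawn, but as written they report platelets only. What is at stake is earlier recognition of a fall in an individual patient, not a treatment comparison.

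**Working it through.** **1. The gap.** Day 6 is the 120 h column of the flow chart, and (6 − 1) × 24 = 120 h reproduces it. Day 3 is (3 − 1) × 24 = 48 h and Day 5 is (5 − 1) × 24 = 96 h. Platelet samples on seven dialysis days, before and after, make 7 × 2 = 14, which matches the maximum of 14 in Table 4. Between Day 1 predose and Day 6 there are 1 + 2 + 2 = 5 platelet samples. Two are pre-dialysis (about 48 h and 96 h). The other three are end-of-dialysis values and are affected by fluid removal.

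**2. Days from a session to the next scheduled hemoglobin.**

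| Session | As written | With Days 3 and 5 pre-dialysis |
|---|---|---|
| Day 1 | 5 | 2 |
| Day 3 | 3 | 2 |
| Day 5 | 1 | 1 |
| Day 8 | 4 | 4 |
| Day 10 | 2 | 2 |

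Only the Day 1 and Day 3 sessions gain. The gap from Day 6 to Day 12, (12 − 6) × 24 = 144 h, is unchanged.

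**3. Which baseline matches.** Protocol 10.1 places Day -7 one week before Day 1, so there is no Day 0. Intervals since the previous dialysis are then:
- Day -5: 2 days
- Day -3: 2 days
- Day 1: 3 days
- Day 3: 2 days
- Day 5: 2 days

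Day 1 predose is therefore likely to be more diluted than Days 3 and 5. Against that baseline a later value could rise through fluid alone and hide a small fall. Days -5 and -3 match.

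**4. How many patients.** Protocol 8.4.1 gives cartridge exchange in 5-7% of heparin-free procedures. Assume independent sessions and no drug effect. Over the two sessions that gain, 1 − 0.95² = 0.0975 and 1 − 0.93² = 0.135. Of 24 patients that is 2.3 to 3.2. If exchanges cluster fully in the same patients it is 0.05 × 24 = 1.2 to 0.07 × 24 = 1.7. If only 8 placebo patients are at risk it is 0.8 to 1.1. An exchange need not mean a 228 mL loss.

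**5. How large a fall.** Assume 10 g/dL, the entry limit, and 4 to 6 L blood volume, which the documents do not give. Fall = 10 × loss / blood volume.
- One loss of 228 mL: 0.57 g/dL at 4 L, 0.46 at 5 L, 0.38 at 6 L.
- Two losses, 456 mL: 1.14, 0.91 and 0.76 g/dL.

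The amendment raised the entry limit by 10 − 8.5 = 1.5 g/dL, so two full circuit losses alone stay inside it. Study blood sampling, which every arm has, comes on top.

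**6. Arm means.** The expected shift per session is 0.05 × 0.38 = 0.019 to 0.07 × 0.57 = 0.040 g/dL, too small to compare arms on.

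**7. Blood cost if the platelet tube cannot be used.** Four pre-dialysis draws at the Table 4 platelet volume: 4 × 3.5 = 14 mL. For every platelet-only time point, 14 less the two shared with hematology (Days 1 and 12) leaves 12, and 12 × 3.5 = 42 mL. Table 4 allows up to 50 mL extra.

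**The case against.** A reader might infer that 13.3 makes a promise which the schedule then breaks. The documents do not support that. The sentence follows directly on the text about a clotted circuit, so it concerns follow-up after a clot. It can be met as written: 13.2.7 allows unscheduled laboratory tests at the investigator's discretion, and "Any nonscheduled procedures required for urgent evaluation of safety concerns take precedence over all routine scheduled procedures". Unscheduled values are listed under SAP 8. Confinement helps too: "Patients will be housed on Day -8, at the time indicated by the CRU, until after completion of study procedures on Day 6".

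Other cover is real as well. Venous pressure is monitored continuously, adverse events are asked about daily, access-site bleeding time is taken after dialysis on Days 1, 3 and 5, and vital signs are taken before dialysis on Days 3 and 5. A clotted dialyzer is seen and replaced without any need for a hemoglobin. The Day 6 value captures cumulative loss, with placebo alongside.

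It is also fair to say that the expected falls are small and that the active-period argument is partial. At 0.25 mg/kg the 48 h value comes after activity is expected to have ended. At 0.5 mg/kg the 96 h value lies beyond the stated minimum of 72 h.

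All of this stands, and it limits the point to a modest improvement. Two things remain. Discretionary testing depends on a prompt, which hidden bleeding may not give. And SAP 8.4 keeps postdose unscheduled results out of the summaries, so values obtained that way would appear only in listings.

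**Conclusion.** The schedule gap is real: about 120 h and three heparin-free sessions without a scheduled hemoglobin, which could fall to about 48 h using samples already drawn. It is an inexpensive safety improvement for individual patients, chiefly for blood loss that prompts no unscheduled test. It is not a breach of 13.3 and not evidence of a hazard. No between-arm gain is claimed.

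A reader might also take the Day 3 and Day 5 values as directly comparable with Day 1 predose. The unequal dialysis interval argues against that, and the matched comparison is with Days -5 and -3.

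The conclusion rests on the schedule as stated in both documents. That the platelet tube can yield hemoglobin is inferred from the shared panel and footnote s; it is not stated. The sizes rest on the assumed blood volume and hemoglobin and on the cited exchange rate.

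**What to change.** - **Flow chart and SAP 8.4:** report hemoglobin and hematocrit from the existing pre-dialysis platelet samples on Days -5, -3, 3 and 5. Add these time points to the hematology table (14.3.5.3) so that hemoglobin stays in one place.
- **Baseline:** for Days 3 and 5, state that change is taken from Days -5 and -3 (for example their mean). The general SAP 8.4 rule would otherwise select Day 1 predose. Body weight is already measured before each session (13.2.4) and can be shown beside the values.
- **Protocol 13.3, as a useful clarification only:** add that hemoglobin will be measured before the next session after a clotted circuit. A Day 5 clot is met by the Day 6 hematology. A Day 10 clot can be met from the Day 12 pre-dialysis platelet sample. A Day 8 clot needs one extra draw of about 3.5 mL before the Day 10 session.

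The cost is wording in two documents, with the approvals that 15.8 requires for a protocol change, and a few more results to review. If the platelet tube cannot be used, it is 14 mL more blood per patient. Using every platelet-only time point could take about 42 mL and is not proposed. For patients without a clot, the Day 6 to Day 12 interval stays as it is.
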